Rationale and Background. GLP-1 RA have been a focus of attention since the signalling of certain (rare but serious) adverse effects potentially associated with their use: acute pancreatitis, pancreatic cancer and thyroid cancer, in particular medullary thyroid cancer. With increasing follow-up time available, it is opportune to examine such associations in high-quality prescription databases.

Research Question and Objectives. This study is designed to focus on the risk associated with use of GLP-1 RA and will investigate the primary hypotheses that adult patients prescribed GLP-1 RA: (1) have an increased risk of acute pancreatitis when compared to patients prescribed other types of anti-diabetic drugs; (2) have an increased risk of pancreatic cancer when compared to patients prescribed other types of anti-diabetic drugs; and (3) have an increased risk of thyroid cancer, in particular medullary thyroid cancer when compared to patients prescribed other types of anti-diabetic drugs. Through this investigation, this study will establish the profile of users of GLP-1 RAs and of other anti-diabetic medications.

Study Design A series of retrospective cohort studies will be conducted based on prescription databases in Denmark, Norway, and Sweden, with a view to country-specific analysis and a planned meta-analysis of the three studies.

Population Everyone prescribed an anti-diabetic medication in Denmark, Norway and Sweden since the day on which the first GLP-1 agonist was approved for use.

Variables For each patient, information regarding all anti-diabetic medications prescribed in the study period will be recorded together with basic information such as age and gender. Patients who develop pancreatic and thyroid cancer, in particular medullary thyroid cancer will be identified as well anyone who is diagnosed with acute pancreatitis.

Data Sources Patients will be identified in the National Prescription Database and will be linked to the National Death Indices, National Cancer Registries and National Hospital Discharge schemes to identify cases of cancer, acute pancreatitis and anyone who has died.

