Spontaneous (post-marketing) reports of acute pancreatitis among type 2 diabetes patients on GLP-1 agonists were submitted to the FDA Adverse Event Reporting System [FDA alert: information for healthcare professionals: exenatide (marketed as Byetta). FDA: Postmarket Drug Safety Information for Patients and Providers, available at: http://www.fda.gov/Drugs/DrugSafety/PostmarketDrugSafetyInformationforPatientsand Providers/ucm124713.htm]. Since the introduction on the market in 2005 until 8/18/2008, 36 cases of acute pancreatitis were reported in patients taking Byetta. As a result of these spontaneous results the FDA required the manufacturer to include a warning for the risk of pancreatitis on the prescribing information of exenatide.

Also, at the introduction on the market of the new molecule liraglutide (marketed as Victoza), patients were warned about the potential risks of pancreatitis, as there was a 4:1 imbalance

http://www.fda.gov/Drugs/DrugSafety/PostmarketDrugSafetyInformationforPatientsand Providers/ucm198543.htm) of the pancreatitis cases in patients using Victoza compared to patients using another diabetes medicine in five clinical trials.

However the preclinical and clinical evidence over the mechanism linking GLP-1 RA and acute pancreatitis is conflicting (Anderson et al, 2010; Elashoff et al, 2011; Drucker et al 2011). Preclinical studies showed equally a negative effect of incretin based drugs on the risk of developing pancreatitis (Matveyenko et al, 2009; Nachani et al, 2010) as well as a null effect or a positive effect (Engel et al, 2010; Tatarliewicz et al, 2010).

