- (2) A high-quality cancer registry, which covers the entire population included in the prescription database.
- (3) A national hospital discharge registry, which covers the entire population included in the prescription database
- (4) A national death register, which can be used for record linkage to ascertain the date of death of any cohort member who died.
- (5) A source of information on key confounders (notably BMI), either in the prescription database itself, in a diabetes registry or in other available databases or large prospective studies.

The study population will include adult T2DM patients in Denmark, Norway and Sweden treated with exenatide or liraglutide (cohort 1) and these groups will be compared with patients treated with other anti-diabetics (cohort 2). Patients with previous diagnosis of the outcomes of interest will be excluded.

A unique personal identity number will be used to link together the information from the several population based registries, as shown in Figure 1:

The source of the cohorts will be mainly represented by the drug prescription registries. Patients with diabetes will be identified as having been prescribed at least one prescription for an anti-diabetic drug, i.e. ATC code 'A10' and subcategories.

High completeness of follow-up is expected, as well as high accuracy of data, which will allow capture of the variables of most interest; this is supported by our previous study (glargine and risk of cancer).

A detailed table of characteristics of the cohort included in the analysis will be provided after consultation with the local investigators.

II.9.3 Variables

The study population will include adult T2DM patients in Denmark, Norway and Sweden treated with exenatide or liraglutide (cohort 1) and these groups will be compared with patients treated with other anti-diabetics (cohort 2).

Patients with the following conditions will be excluded from the study:

1) Individuals less than 18 years of age at the cohort entry;

2) Individuals with a diagnosis of thyroid cancer, pancreatic cancer, or any pancreatitis prior to cohort entry.

Dates

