All patients who appear in the prescription registries of the countries with a record of prescription for anti-diabetes medication between the start date and end date for the centre are included in the analysis. Any patient without a record of prescription of any type of anti-diabetic medication will be excluded, as well as patients younger than 18 years at their start date. Patients with a cancer diagnosed prior to their start date (3) months after their date of first receiving anti-diabetic medication) will be excluded in the analysis as it is very unlikely that the cancer could be associated with the anti-diabetic treatment. We exclude the first 3 months from the beginning of anti-diabetes treatment because of the possibility that diabetes was caused by (or diagnosed following clinical workup for) cancer (reverse causality). As three months may be considered rather short and arbitrary length of the immortal time period to be excluded, a sensitivity analysis for exclusion of 6 months immortal time will be done. An eligible diabetes prescription is defined as only those occurring three months (or six months) or more before the censoring date (cancer, death and last date in registry). However, the three month (or six months) window will not apply for patients diagnosed with acute pancreatitis where, theoretically, this could be a rapid and acute response to an external stimulus such as therapy.

The starting date for an individual in the study is the date of first prescription of either exenatide or liraglutide for cohort 1 or the date of first prescription of other antidiabetics (e.g., oral anti-diabetics, insulins) for cohort 2 during the study period.

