Patients who cease glargine/detemir will remain in their highest attained dose group for the duration of follow up.

*Dose response will be calculated for glargine and detemir; it will not be calculated for non long acting insulins.

Stratification

- Age Group at the beginning of the Patient Prescription Registry opening in 10 year age bands (<34, 35-44, ..., 65-74, 75+.). The follow up is not so long that it is necessary to have age group as a time dependent effect.
- Sex.
- Type of Diabetes, Type I and Type II separately.

Allocation bias

Allocation bias is the big problem and to control this (partly) Type 1 and Type 2 patients will be analysed separately. Adjustment for differences between Type 1 and Type 2 diabetics are likely to lead to more complex interaction models and it is simpler to fit separate models for each type and use a meta regression model to investigate if the effect of ever taking glargine on cancer risk is the same in type 1 patients compared to type 2.

Patients who take glargine on its own must be Type 2.

Type 1 patients can be of any age though age at first insulin below 35 is a good proxy for type 1

Type 1 patients more likely to have glargine are the relatively healthy and active.

Type 2 patients more likely to be on glargine are elderly, frail, and not coping on other insulins.

Confounders (most measured on study)

These will not be the same in all centres though if it is possible to identify a minimal set which are available then the following model will be used.

There will be missing values for the covariates. Imputations will be used.

But we have to make sure that multiple imputation should be conducted only if missing values represent a small proportion of the dataset. We should not apply it for variables missing in 50-90% of individuals.

Within each centre there will require to be the assessment of whether or not a potential confounder variable does require being in the model. Possible confounders are smoking status, deprivation etc,

Type of insulin regimen is associated with unmeasured confounders.

Age at the birth of the first (live?) child might be used for breast cancer over and above the variables used in the previous analysis.

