Appendix V

ATC List of Anti-Diabetic Drugs

A10 - Drugs used in diabetes* A10A - Insulins and analogues

A10AB - Insulins and analogues for injection, fast-acting

- A10AB01 Insulin (human)
- A10AB02 Insulin (beef)
- A10AB03 Insulin (pork)
- A10AB04 Insulin lispro
- A10AB05 Insulin aspart
- A10AB06 Insulin glulisine
- A10AB30 Combinations

A10AC - Insulins and analogues for injection, intermediate-acting

- A10AC01 Insulin (human)
- A10AC02 Insulin (beef)
- A10AC03 Insulin (pork)
- A10AC04 Insulin lispro
- A10AC30 Combinations

A10AD - Insulins and analogues for injection, intermediate-acting combined with fast-acting

- A10AD01 Insulin (human)
- A10AD02 Insulin (beef)
- A10AD03 Insulin (pork)
- A10AD04 Insulin lispro
- A10AD05 Insulin aspart
- A10AD30 Combinations

A10AE - Insulins and analogues for injection, long-acting

- A10AE01 Insulin (human) A10AE02 - Insulin (beef) A10AE03 - Insulin (pork) A10AE04 - Insulin glargine
- A10AE05 Insulin detemir
- A10AE30 Combinations

A10AF - Insulins and analogues, for inhalation

A10AF01 - Insulin (human)

A10B - Blood glucose lowering drugs, excluding insulins

A10BA - Biguanides

A10BA02 - Metformin

A10BB - Sulfonamides, urea derivatives

A10BB12 - Glimepiride

A10BD - Combinations of oral blood glucose lowering drugs

- A10BD03 Metformin and rosiglitazone
- A10BD04 Glimepiride and rosiglitazone
- A10BD05 Metformin and pioglitazone
- A10BD06 Glimepiride and pioglitazone
- A10BD07 Metformin and sitagliptin
- A10BD08 Metformin and vildagliptin
- A10BD11 Metformin and linagliptin

A10BG - Thiazolidinediones

- A10BG02 Rosiglitazone
- A10BG03 Pioglitazone

A10BH - Dipeptidyl peptidase 4 (dpp-4) inhibitors

- A10BH01 Sitagliptin
- A10BH02 Vildagliptin
- A10BH03 Saxagliptin
- A10BH05 Linagliptin

A10BX - Other oral blood glucose lowering drugs

- A10BX02 Repaglinide
- A10BX03 Nateglinide
- A10BX04 Exenatide
- A10BX06 Benfluorex
- A10BX07 Liraglutide

*Source: http://ec.europa.eu/health/documents/community-register/html/atc.htm

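### The population is declared as adult type 2 diabetes, but the inclusion rule takes every adult with an A10 prescription and no rule identifies type 1, so type 1 adults enter cohort 2 and the Registry's insulin background rate.

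*Protocol*

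**What the plan says.** The declared population is type 2. Sections II.9.2 and II.9.3 both state: "The study population will include adult T2DM patients in Denmark, Norway and Sweden treated with exenatide or liraglutide (cohort 1"), to be compared with patients on other anti-diabetics (cohort 2). The objectives in II.8 are worded for adult type 2 patients in both groups. Section II.9.5 takes 5% type 2 prevalence in 15,000,000 adults to reach 750,000 subjects.

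The rule that selects people is wider:

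- The Part II synopsis gives the population as "Everyone prescribed an anti-diabetic medication in Denmark, Norway and Sweden since the day on which the first GLP-1 agonist was approved for use".
- Section II.9.2 says: "Patients with diabetes will be identified as having been prescribed at least one prescription for an anti-diabetic drug, i.e. ATC code 'A10' and subcategories".
- Section II.9.3 (Dates) says: "All patients who appear in the prescription registries of the countries with a record of prescription for anti-diabetes medication between the start date" and the end date are included in the analysis. It starts cohort 2 at the first prescription of another anti-diabetic and names insulins as an example.

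The exclusions in II.9.3 are age under 18, a previous outcome diagnosis (thyroid cancer, pancreatic cancer or any pancreatitis), a cancer before the start date, and no anti-diabetic prescription. Diabetes type is neither a listed covariate in II.9.3 nor a named stratum in II.9.7.

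Appendix III, the plan of the earlier glargine study, does deal with type. It analyses type 1 and type 2 separately, excludes gestational diabetes where a diabetes registry identifies it, lists a type 2 restricted sensitivity analysis, and offers a proxy: "Type 1 patients can be of any age though age at first insulin below 35 is a good proxy for type 1". Section II.9.7 adopts that plan only in spirit.

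In the Registry, III.9.7 takes expected counts from the Database Study's background rates. Hypotheses 4 to 6 in III.8 split the comparator into oral drugs and insulin and treat insulin as a marker of more severe diabetes.

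**The concern.** A programmer in each country who follows II.9.2 and II.9.3 will extract all adult A10 users. GLP-1 receptor agonists are indicated in type 2 diabetes (II.7), so cohort 1 is in effect type 2, while cohort 2 mixes types. Any difference in event rates between type 1 and type 2 then enters the contrast for a reason unrelated to treatment.

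Three results are exposed: the cohort 2 incidence rates, which are a primary objective; the hazard ratios; and the expected counts for Registry hypotheses 4 to 6. The insulin group is the most exposed. Type 1 patients concentrate there, and reading insulin as a sign of severity does not hold for them.

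Under II.9.6 only model coefficients leave each country, so the coordinating centre cannot correct a wrong cohort definition afterwards.

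**Working it through.** **Reproducing the plan's own figures.** Inputs from II.9.5: rates of 65.57, 29.19 and 6.13 per 100,000 person-years, 90% power, and 37,000 or 74,000 exposed person-years out of 750,000, leaving 713,000 or 676,000 unexposed. Solve for r in

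(r − 1)λ / √(λr/t₁ + λ/t₀) = z(0.95) + z(0.90).

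| Exposure | Table II.9.5.2 | Recomputed |
|---|---|---|
| 5% | 1.80 / 2.40 / 5.63 | 1.81 / 2.39 / 5.63 |
| 10% | 1.54 / 1.89 / 3.67 | 1.54 / 1.89 / 3.67 |

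The match needs a one-sided 5% test; the protocol does not state the sidedness. The total behind the table is a type 2 population, so the calculation describes a different cohort from the one the A10 rule selects.

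**Effect of a mixed comparator on the hazard ratio.** Let p be the type 1 share of comparator person-time and k its event rate relative to the rest of the comparator. Neither is in the documents. The hazard ratio is multiplied by 1 / (1 − p + pk). Over assumed ranges, before any stratification:

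| p | k = 0.2 | k = 0.5 | k = 1 | k = 2 |
|---|---|---|---|---|
| 5% | 1.04 | 1.03 | 1.00 | 0.95 |
| 10% | 1.09 | 1.05 | 1.00 | 0.91 |
| 30% | 1.32 | 1.18 | 1.00 | 0.77 |

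**Effect on a Registry signal.** Take 38 truly expected pancreatitis cases (Table III.9.5.1, 1% exposure), no drug effect, and a one-sided exact Poisson test at 0.05. The expected count actually used is 38 × (1 − p + pk). The last column is the chance of reaching the threshold when the true mean is 38.

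| p, k | Expected count used | Signal threshold | False signal |
|---|---|---|---|
| none | 38.0 | 49 | 4.9% |
| 10%, 0.5 | 36.1 | 47 | 8.7% |
| 30%, 0.5 | 32.3 | 43 | 22.9% |
| 30%, 0.2 | 28.88 | 39 | 45.7% |

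With k above 1 the expected count is too high and a real signal is harder to see.

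**Cost of restricting cohort 2.** Removing 10% or 30% of unexposed time at 5% exposure gives detectable risks of 1.81 / 2.39 / 5.64 or 1.82 / 2.40 / 5.65, against 1.81 / 2.39 / 5.63 with none removed.

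**The case against.** The strongest defence is that the planned analysis already limits the damage. II.9.3 says all analyses are stratified by age, gender and treatment history, and II.9.7 repeats this. II.7 describes liraglutide in Europe as used in combination with oral agents, so insulin-only type 1 patients would tend to fall in strata with few or no GLP-1 users, and a stratum without exposed patients adds nothing to a stratified Cox estimate. The favoured new-user approach also drops most long-standing insulin users. This stands in part. The new-user approach is favoured but not fixed, and the strata are not defined. Previous insulin use does not separate type 1 from insulin-treated type 2, and adults newly starting insulin for type 1 still enter.

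A second defence is that the declared type 2 population governs and that a later analysis plan could supply the algorithm. But the protocol itself states two different populations, and that conflict needs resolving here.

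A reader might also infer that DPP-4 inhibitor users are wrongly placed in the comparator. Appendix V lists "A10BH - Dipeptidyl peptidase 4 (dpp-4) inhibitors" under A10, and II.7 says: "Preclinical studies showed equally a negative effect of incretin based drugs on the risk of developing pancreatitis". The documents do not support calling this an error. The declared hypotheses compare GLP-1 agents with other types of anti-diabetic drugs, which DPP-4 inhibitors are. The same sentence in II.7 goes on to report null and favourable preclinical findings, and that paragraph calls the evidence conflicting. If DPP-4 inhibitors carried the same ratio of 1.5 (assumed), a true 1.5 would read 1.5 / (1 + 0.5f), that is 1.46, 1.43 or 1.36 at shares f of 5, 10 or 20%. Without a shared effect there is no bias. Removing them from the primary comparator changes the question and is a debatable trade-off.

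**Conclusion.** The point holds as a contradiction between the declared type 2 population and the A10 rule, with no type 1 or gestational diabetes rule fixed for this study. As written, type 1 adults on insulin enter cohort 2 and the Registry's insulin background rate. This can bias the GLP-1 contrast and Registry hypotheses 4 to 6. Hypotheses 1 to 3 compare lixisenatide with other GLP-1 users and are not affected.

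It would go too far to say that the hazard ratios are distorted by a known amount. Every share and rate ratio above is an assumption, the result runs from nil to large in either direction, and stratification and the new-user approach take away part of it. This is a change that should be made because the rule is wrong on its face and the remedy is cheap, not because a particular bias has been shown.

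**What to change.** In II.9.3, reconcile the A10 rule with the type 2 population by carrying over the Appendix III handling:

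- Exclude, or analyse separately, patients with a registry diagnosis of type 1 or, where first insulin is observable, insulin-only patients whose first insulin came before age 35.
- Exclude gestational diabetes where it can be identified.
- Use the same type 2 restricted groups for the Registry background rates.
- Keep the all-A10 contrast as a sensitivity analysis, and bring the synopsis and II.9.2 into line.

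Optionally, add a sensitivity analysis that shows DPP-4 inhibitor users as a separate comparator stratum.

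The cost is protocol wording, code in three centres and a little comparator person-time, with almost no loss of power. The proxy is imperfect: Appendix III itself notes that type 1 can occur at any age. It also cannot be applied to prevalent users whose first insulin predates the prescription register, so the report should state how many patients remain unclassified.

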A new user approach will be favoured in order to reduce prevalent user bias and confounding from covariates that could be associated with drug use (Ray, 2003). New users are defined as patients who initiated **either GLP-1 treatment or other antidiabetic drugs** at least 6 months after the start date of the study (this will include patients who are treatment naive in regards to any anti-diabetic medication although this group will be very few in numbers). The 6 months 'criterion' was defined in previous work on these databases (Boyle et al, 2013). Figure II.9.3.1 shows possible patient trajectories; incident users (with no history of anti-diabetic treatment) are patients 5, 6 and 7 on this diagram. As all prescription databases were set up relatively recently (i.e. 2004-2005), and we will have many patients in the cohort that developed diabetes long before that, the new user approach will deal with patients for whom we have complete data on the history of anti-diabetic medication.

The period of follow-up begins at that time or three months later until a specified event takes place, either (1) date of cancer/or acute pancreatitis diagnosis; (2) date of death (right censoring, only if death occurred before the last date of available data in registry); and, (3) last date of available data in cancer registry.

Figure II.9.3.1: possible patient trajectories

Acute pancreatitis cases will be identified from the hospital discharge registers. The diagnosis of acute pancreatitis is a clinical diagnosis that hinges on the presence of abdominal pain and elevation of two biomarkers, themselves not diagnostic. One potential issue to be faced is that abdominal pain can be an unwanted side effect of the use of GLP-1 medication and this could lead to diagnostic bias.

Cases of all thyroid cancers (especially medullary thyroid cancer) and pancreatic cancer will be identified from the national cancer registers. However, data on the cancer cases for a given year are typically considered incomplete until approximately one year after the year ends. Therefore, it will be possible to use the national cancer registries in these three countries to identify incident cancers occurring until the end of 2012, if the analysis of thyroid cancer is planned to be performed in early 2014.

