All models to be fitted on all da	ta and the subset	of Type 2 dia	betes only			
In some centres Type 2 diabete	s will only be pre	sumed from				
date of first prescription and so	only for the PNH	IP6M dataset				

The above analysis will be applied to each cancer site defined in Appendix 2: ICD codes.

The comparison of glargine against all other insulin will represent the main analysis since it is defined as the main endpoint in the operational protocol. Further analysis in order to identify if an increase risk of cancer is observed for long acting insulin separating glargine from long acting non glargine insulin will be conducted. An analysis will be conducted to compare glargine to other LANG, which is the most equivalent group to glargine (same indication for treatment).

Common steps:

- Starting date: first use of insulin following the introduction of Glargine in the country

- Follow-up: until either (1) date of cancer, (2)date of death (right censoring, only if death occurs before the last date of available data in cancer registry), (3) last date

of available data in cancer registry (right censoring, this date will be similar to most individuals in the study)

- Eligible insulin prescription: only those occurring 3 month or more before the censoring date (cancer, death, and last date in registry).

- All prescription dates should be shifted by 3 months for each individual, then usual data management should be conducted to classify individuals (i.e. a cancer occurring before the first prescription is not included). This will avoid including an immortal time bias since both events and person-years are removed from the 3 month period.

- Method: Cox proportional hazard model with time dependent variable for exposure variable

- Analysis stratified on gender and age group * => allowing different underlying hazard functions for each stratum.

- Analysis is also adjusted systematically for metformin use included in the model as a time dependent variable. The metformin variable will be entered as an ever/never variable.

*Age groups: <35, 35-44, .., 65-74, 75+.

Sensibility analysis

s – 1– Latency **

s - 1 - 1: Analysis restricted to Patients with No History of Insulin in the Previous 8 Months (PNHIP8M)

s - 2- 2: Analysis restricted to Patients with No History of Insulin in the Previous 12 Months (PNHIP12M)

s – 2– Restricted to type II diabetes**

s – 3– Adjusted for covariates**

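### For the two cancer outcomes, II.9.3 pairs a backward prescription window with no stated lag after the first GLP-1 RA prescription, which can bias the hazard ratio downwards

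*Protocol*

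**What the plan says.** Protocol section II.9.3 (Variables, Dates) contains five statements that bear on this.

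- Prescriptions count by looking back from the end of observation: "An eligible diabetes prescription is defined as only those occurring three months (or six months) or more before the censoring date". The end may be cancer, death or the last registry date.
- The reverse-causality exclusion is tied to the first anti-diabetic drug of any kind: "We exclude the first 3 months from the beginning of anti-diabetes treatment because of the possibility that diabetes was caused by" the cancer, or found during its work-up. A sensitivity analysis lengthens the window: "a sensitivity analysis for exclusion of 6 months immortal time will be done".
- Entry to the exposed cohort carries no lag: "The starting date for an individual in the study is the date of first prescription of either exenatide or liraglutide for cohort 1".
- The start of follow-up has two alternatives: "The period of follow-up begins at that time or three months later until a specified event takes place". The text does not say when each applies.
- Acute pancreatitis is exempt: "the three month (or six months) window will not apply for patients diagnosed with acute pancreatitis".

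On treatment-naive new users, the same section remarks "although this group will be very few in numbers". Most GLP-1 RA starters will therefore already have been on another drug.

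Appendix III, the analysis plan of the earlier glargine study, has the same backward rule for insulin under Common steps. There it is followed by a second rule: "All prescription dates should be shifted by 3 months for each individual". The appendix says that the shift prevents immortal time bias, because events and person-years both leave the window. Its section on person time at risk applies the three months to every new insulin. Section II.9.7 says the present analysis will follow that plan in spirit, with full details to come.

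**The concern.** A rule that looks back from the event makes exposure depend on the future. Take a patient on metformin who starts a GLP-1 RA and has a cancer diagnosed two months later. The GLP-1 RA prescription is not eligible, so the case goes to the comparator or is lost. A patient who starts on the same day and stays cancer-free keeps those two months as exposed time, if exposed time runs from the first GLP-1 RA prescription.

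The stated three-month exclusion does not cover this patient, because it runs from the first anti-diabetic drug and ended before the switch. The forward shift implies the backward rule, but the backward rule does not imply the shift.

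The bias would be towards a lower hazard ratio in a study whose purpose is to find harm. The six-month sensitivity analysis would be more distorted than the main analysis it is meant to check.

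**Working it through.** **Inputs.** From II.9.5: 750,000 diabetic patients, 37,000 GLP-1 RA person-years at 5% exposure and one year of mean follow-up, and a pancreatic cancer rate of 29.19 per 100,000 person-years. From Table II.9.5.2: a minimum detectable ratio of 2.40 for pancreatic cancer at 90% power. Lags L of 0.25 and 0.5 years are from II.9.3. Assumed: constant hazards, and a comparator not distorted by the same rule.

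**1. The plan's own figures.** A one-sided 5% Wald test on the difference of two Poisson rates, with t1 = 37,000 or 74,000 and t0 = 750,000 − t1, reproduces Table II.9.5.2 (stated values in brackets):
- 5% exposed: 1.81 (1.80), 2.39 (2.40), 5.63 (5.63)
- 10% exposed: 1.54 (1.54), 1.89 (1.89), 3.67 (3.67)

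The table is used only as an anchor.

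**2. Null ratio under the backward rule, exposed time counted from the first GLP-1 RA prescription.** Let F be the mean GLP-1 RA follow-up in years.
- Everyone followed for exactly F: ratio = (F − L)/F.
- Exponential follow-up: patients whose follow-up ends within L lose their exposure altogether. The rest have mean time F + L, of which only F can yield an exposed cancer. Ratio = F/(F + L).

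| F | L = 0.25, fixed | L = 0.25, exponential | L = 0.5, fixed | L = 0.5, exponential |
|---|---|---|---|---|
| 1 | 0.75 | 0.80 | 0.50 | 0.67 |
| 2 | 0.88 | 0.89 | 0.75 | 0.80 |
| 3 | 0.92 | 0.92 | 0.83 | 0.86 |

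These figures drop the early cases. Moving them to the comparator changes little. At F = 1 and L = 0.25, the expected exposed cases are 37,000 × 29.19/100,000 = 10.8, of which 2.7 move. The exposed rate becomes 8.1/37,000 = 21.9 per 100,000. The comparator rate becomes (208.0 + 2.7)/712,500 = 29.6 per 100,000. The ratio is 0.74 (0.49 with six months).

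**3. With the Appendix III shift.** Cases and person-time both leave the window: (10.8 − 2.7)/(37,000 − 9,250) = 29.2 per 100,000, a ratio of 1.00.

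**4. Simulation under the null.** 2,000,000 patients were followed for up to five years, with 20% switching to a GLP-1 RA at a uniform time in the first four years (mean GLP-1 RA follow-up 2.93 years). The switch times and event rate are assumptions.

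| Rule | 3 months | 6 months |
|---|---|---|
| No lag | 1.00 | 1.00 |
| Backward rule only | 0.90 | 0.81 |
| Forward shift | 1.00 | 1.00 |
| Backward rule, cohort 1 follow-up from one lag after first GLP-1 RA prescription | 0.99 | 0.98 |

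With switches allowed up to year five (mean follow-up 2.46 years), the backward rule gives 0.88 and 0.79 and the last row 0.98 and 0.97. No lag gives 0.99 in that run.

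**5. Power, fixed one-year follow-up (the least favourable case).** At a true ratio of 2.40 for pancreatic cancer and a three-month lag, the exposed rate is 70.06 × 0.75 = 52.54 per 100,000. The 6.5 cases that move raise the comparator rate to 30.10. The expected ratio is 1.75 and power is 58%; with the shift they are 2.40 and 82%. With six months the backward rule gives 1.13 and 11%; the shift gives 2.40 and 67%.

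**The case against.** A reader might infer that the protocol, as written, makes the first months of GLP-1 RA exposure immortal, that a true hazard ratio of 1 will appear as 0.75 or 0.50, and that the sponsor discarded the Appendix III safeguard. The documents do not support that.

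- **A forward start is in the text.** With acute pancreatitis exempt, a coherent reading is an immediate start for pancreatitis and a start three months later for cancer. The nearest antecedents for the start are the first GLP-1 RA prescription and the initiation of GLP-1 treatment. On that reading the ratio is 0.98 to 0.99. This stands, and it makes the bias conditional. However, the protocol does not state the reading, and three national centres run the individual-level analyses separately.
- **The intent is clear.** II.9.3 calls the window immortal time to be excluded, and II.9.7 takes Appendix III as its model. The shift is unstated, not rejected. This stands too.
- **It could be left to an analysis plan.** This stands only in part. The protocol itself fixes the eligibility rule, the entry date and the anchor of the exclusion, so a later plan would have to override them.
- **The largest figures are worst cases.** 0.75 needs identical follow-up for all, and 0.50 belongs to the sensitivity analysis. One year is a deliberately conservative power assumption, while cancer follow-up runs from November 2006 to December 2012. If cohort 2 starters were counted in the same way, part of the distortion would cancel. All of this stands, and the sizes are given as ranges for that reason.

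**Conclusion.** The concern holds conditionally, for pancreatic and thyroid cancer only. II.9.3 combines a backward eligibility rule, an unlagged cohort 1 entry and an exclusion anchored on the wrong event for switchers, and it does not settle when follow-up begins. If exposed time runs from the first GLP-1 RA prescription, the null ratio is about 0.75 to 0.80 at one year of mean follow-up and about 0.9 at two to three years with the three-month lag. With six months it is about 0.50 to 0.67 at one year and 0.75 to 0.86 at two to three years. If the later start runs from the first GLP-1 RA prescription, little bias remains.

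The sizes rest on constant hazards, an undistorted comparator and, for the lower end of each range, every user being followed beyond the lag. The direction, towards hiding harm, does not depend on the exact size. This should be resolved before the centres build their analysis files.

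**What to change.** In II.9.3, replace the backward eligibility sentence for the cancer outcomes. Every new exposure start, including a switch to a GLP-1 RA, is moved forward by three months (six in the sensitivity analysis) as in Appendix III, with events and person-time in that window handled alike in both cohorts.

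Align the follow-up sentence by saying which start applies to which outcome, and from which prescription the lag is counted.

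Reword the pancreatitis exemption so that it covers the acute pancreatitis analysis for all patients. As written it is limited to patients who receive the diagnosis, which again conditions on the outcome.

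The cost is a few sentences. The method is the sponsor's own and needs no new data. Some exposed person-time is given up for the cancer analyses: 9,250 of 37,000 person-years at one year of follow-up and a three-month lag.
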